Parents/carers within the same family will be randomised to the same arm, making this a cluster RCT, given responses within the same family are potentially highly correlated. We might expect, based on our previous research with families, an average cluster size within families of up to a maximum of 1.5 parents and a high degree of correlation among parents/carers from the same family, so also allow for an ICC=0.5 (Davé et al., 2008). Following Teerenstra et al. (2012), we also allow for a correlation between baseline and follow-up measures of primary outcome of $r=0.5$ (this is a conservative estimate based on published SDQ test-retest correlations between 0.74-0.84; Nowak et al., 2008). The sample size is then inflated to account

for 20% of families being lost to follow-up at the 12-month post-randomisation follow-up time point.

Allowing for the above assumptions and an effect size to be detected of 0.35 with 90% power and a two-sided alpha of 0.05, a sample size of N=412 (N1 =206, N2=206) is required.

The choice of effect size was based on meta-analytic effects from similar parenting programmes' meta-analyses and on the basis that similar Triple P programmes report large effect sizes that are typically >0.5, some as large as 0.8. On this basis, we reduced to 0.35 given the unique nature of the population in this trial. Further evidence based on individually delivered teen parenting programmes was quite challenging to find well powered RCTs or meta-analyses, so meta-analyses that were slightly outside our age range were also considered.

An efficacy trial for standard teen Triple P report an effect of $d=0.62$ (Salari et al, 2014). In the other meta-analyses, it was also generally around $d=0.6$. Given that we are delivering this to a slightly different population, the current planned MDES 0.35 is justifiably conservative (mainly as most studies have been quite small and in a very different population). Considering the MDES from a clinically meaningful effect size, $d=0.35$ equates approximately to a 2-point change on our primary outcome, an effect smaller than this is unlikely to provide any meaningful change. With reference to sample size and secondary outcomes, the trial is currently powered on the basis of detecting an appropriate MDES for the primary outcome which is standard practice in all major trials (CONSORT statement; Schulz et al., 2010).

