All participants (in both trial arms) will complete assessments at baseline (prior to randomisation), 6- and 12-months post-randomisation and will be given a choice of how these are completed. These assessments can be completed in a number of ways, face-to-face, online on a website, via telephone, via videoconferencing, or on paper via the post. Participants, parents/guardians, young people and key stakeholders will be invited to participate in semi-structured interviews to ascertain acceptability and their experience of

the parenting programme and being in the trial. We will interview a sample of those randomised to each arm of the trial.

Randomisation

Families will be randomised with equal probability to either the intervention or comparator arm using random permuted blocks (block size 4), stratified by local authority site. The statistician doing the analysis will be blind to the treatment allocation. As the families and practitioners are not blind to treatment allocation (as this would be impossible given the intervention), there is no issue in terms of predictability.

Sample size

Sample size calculations were conducted using R version 4.1.2 (2021-11-01), and the 'pwr' R package.

Parents/carers within the same family will be randomised to the same arm, making this a cluster RCT, given responses within the same family are potentially highly correlated. We might expect, based on our previous research with families and consultation with the TMG (Trial Management Group), an average cluster size within families of up to a maximum of 1.5 parents and a high degree of correlation among parents/carers from the same family, so also allow for an ICC=0.5 (Davé et al., 2008). Following Teerenstra et al. (2012), we also allow for a correlation between baseline and follow-up measures of primary outcome of $r=0.5$ (this is a conservative estimate based on published SDQ test-retest correlations between 0.74-0.84; Nowak et al., 2008). The sample size is then inflated to account for 20% of families being lost to follow-up at the 12-month post-randomisation follow-up time point.

Allowing for the above assumptions and an effect size to be detected of 0.35 with 90% power and a two-sided alpha of 0.05, a sample size of $N=412$ ($N_1=206$, $N_2=206$) is required.

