Baseline and 6-month follow up data will only be used in the primary analysis. The 12 month follow up data will be used both in the addendum primary analysis and in an additional follow up analysis including all three time points in a linear mixed model (see section 6.4 – longitudinal follow up analyses). The SDQ consists of 25 items which are each scored on a 3-point Likert scale (0, 1, 2). Externalising scores - Ranges from 0-20 and is generated by summing the scores of the conduct and hyperactivity subscales.

List of secondary outcomes

Secondary outcome measures include:

- Emotional and behavioural difficulties and prosocial behaviour: the Parent report and adolescent self-report versions of the Strengths and Difficulties Questionnaire (SDQ) will be used (including internalising, externalising, peer relationship, and prosocial behaviours). The SDQ is a robust and well-validated measure of behavioural and emotional problems (Deighton et al., 2014); measured over the preceding 6 months.
- Parenting practices: Parenting Scale Adolescent version (PSA, parent completed) is a short form of the Parenting Scale (Irvine et al., 1999) which assesses dysfunctional discipline practices in parents. It is an adaptation of the Parenting Scale (Arnold, et al., 1993) for parents of adolescents
- Interparental outcome - Dyadic Adjustment Scale (DAS-7) is a 7-item measure (Sharpley & Cross 182; Hunsley et al., 2001) assessing the relationship quality of couples. The DAS-7 assesses relationship satisfaction and the degree to which the couple agrees on matters of importance to the relationship.
- Parent mental health – the Kessler Psychological Distress Scale (Kessler 6) is a six-item screening tool for serious mental illness in the general population (Kessler et al., 2003). It will be completed by parents.
- Parent Wellbeing - The Warwick-Edinburgh Mental Well-being Scale (SWEMWBS) is a measure of mental wellbeing (Tennant et al., 2007). The short (7 item) version will be completed by parents.
- Conflict Behavior Questionnaire (CBQ-20) (Robin & Foster, 1989) assesses adolescent-parent communication, conflict and relations. Both the adolescent and parent report versions will be completed.
- Child-parent relationship – the Closeness subscale of the Child-Parent Relationship Scale (CPRS, short form) measures (Pianta, 1995) will be completed by parents.

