For continuous outcome measures, the effect size and 95% confidence interval will be calculated using given in Hedges (2007) for cluster randomised designed analysed via multilevel models and allowing for unequal cluster sizes. According to the two-level LMM for primary outcome given that we have individuals nested within family, a sample estimate of the effect size equivalent to Hedges' g with 95% confidence interval is defined as:

$$\hat{\Delta}_g = \frac{\widehat{\beta}_1}{S_T} \sqrt{1 - \frac{2(n-1)\rho}{N-2}}$$

Where $\widehat{\beta}_1$ is the adjusted mean difference in SDQ externalising score between trial arms; S_T is the within group pooled standard deviation

$$S_T^2 = \frac{\sum_{i=1}^{m^I} \sum_{j=1}^{n_i^I} (Y_{ij}^I - Y_{i..}^I)^2 + \sum_{i=1}^{m^C} \sum_{j=1}^{n_i^C} (Y_{ij}^C - Y_{i..}^C)^2}{N-2}$$

Where ' m ' is the total number of families in the intervention sample, and ' n ' the total number of parent/carers (equivalent definitions apply for the control group, but with the 'C' designation). $Y_{i..}^I$ and $Y_{i..}^C$ are the mean outcomes among intervention and control families respectively.

The remaining part of the $\hat{\Delta}_g$ equation makes the adjustment for clustering. The two intra-class correlation coefficients at the family (ρ) level are defined as follows,

$$\rho = \frac{\sigma_B^2}{\sigma_B^2 + \sigma_W^2} = \frac{\sigma_B^2}{\sigma_T^2},$$

where σ_B^2 is the between-family variance, and σ_W^2 is the within-family variance

If outcomes are categorical, counts or binary, the effect sizes will be reported as odds ratios or incident rate ratios. All parameter estimates from the models will be reported with 95% confidence intervals.

We will report the ICC from the two-level model which is defined as:

$$ICC = \frac{\sigma^2_{family}}{\sigma^2 + \sigma^2_{family}},$$

where σ^2 is the residual variance, and σ^2_{family} is the random intercept variance according to family (family level clustering).

Covariate adjustment

We will assess any imbalance of baseline covariates for possible inclusion in the model where large imbalances are noted. However, due to the sample size, we do not anticipate substantial issues in this respect.

Assumption checking

1. Linearity – plotting residuals vs predictor(s). If a structure is present, then transformation or an alternate model specification is required (i.e. GLMM).

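### The SAP's effect-size formula defines n as all parents in the arm instead of parents per family, so a true effect of 0.35 would be reported as about 0.25

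*SAP*

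**What the plan says.** The SAP, under Secondary outcomes analysis, sets out the standardised effect for the primary outcome and every other continuous outcome, and the longitudinal section reuses Hedges' g at 12 months. The formula is (β̂₁ / S_T) × sqrt(1 − 2(n−1)ρ/(N−2)), with the square root described as the clustering adjustment. The verbal definition of n is "the total number of parent/carers (equivalent definitions apply for the control group".

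S_T is printed as a sum of squared deviations from means that carry the family index i, over N−2. The text says that these means "are the mean outcomes among intervention and control families respectively". The numerator is labelled β̂₁ and described as the adjusted difference between arms.

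On scale, both documents say in their sample size sections that d = 0.35 "equates approximately to a 2-point change on our primary outcome, an effect smaller than this is unlikely to provide any meaningful change". For the externalising score the SAP says: "Ranges from 0-20 and is generated by summing the scores of the conduct and hyperactivity subscales". Neither document states an SD for that score.

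**The concern.** A correction for clustering should depend on how many parents share a family. The definition given makes it depend on how many parents are in the arm. An analyst who codes the text as it stands would shrink every standardised effect by a large factor. The results could then not be compared with the plan's own target of 0.35 or with the published values of about 0.6 that the plan cites as benchmarks.

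Two notational faults sit in the same formula. The family-indexed mean in S_T leaves the centring unclear. The label β̂₁ also clashes with the primary model, where β₁ is the slope on baseline SDQ and treatment is γ₂₀.

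The 2-point statement is a separate, lesser matter. It is the plan's clinical argument for the target effect, and the SD that it needs is not stated.

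**Working it through.** **Inputs (SAP, Sample size).** The target is "an effect size to be detected of 0.35 with 90% power and a two-sided alpha of 0.05". Family size is "up to a maximum of 1.5 parents" on average. For correlation within families the plan says "so also allow for an ICC=0.5". The "correlation between baseline and follow-up measures of primary outcome" is set at 0.5. Loss is 20% of families, and N is 412 (206 per arm).

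**The plan's own figure.**
- A two-sample t-test for 0.35 needs 172.5, so 173 per arm.
- Design effect: 1 + (1.5−1)×0.5 = 1.25. Baseline adjustment: 1 − 0.5² = 0.75.
- 173 × 1.25 × 0.75 = 162.2 parents; /1.5 = 108.1, so 109 families; /0.8 = 136.25, so 137 families; × 1.5 = 205.5, so 206 parents per arm and 412 in total.

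The sample size reproduces exactly. It uses d, not points.

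**What n must be.** Take an arm with N/2 parents in families of size n, total variance σ² and ICC ρ. The expected sum of squares about the arm mean is σ²[N/2 − 1 − (n−1)ρ]. Adding two arms and dividing by N−2 gives E[S_T²] = σ²[1 − 2(n−1)ρ/(N−2)]. This is the term under the SAP's square root. It holds only with n as family size and S_T centred on arm means.

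**n as defined, counted per arm.** With n = N/2, 2(n−1)/(N−2) = 1, so the factor is sqrt(1−ρ) at any sample size. For n = 206 and N = 412:

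| ρ | factor | 0.35 reported as |
|---|---|---|
| 0.3 | 0.837 | 0.29 |
| 0.5 | 0.707 | 0.25 |
| 0.7 | 0.548 | 0.19 |

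After 20% loss (n = 165, N = 330) the factor at ρ = 0.5 is still 0.707.

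**n as defined, counted over both arms.** With n = 412 and ρ = 0.5, the term under the root is 1 − 2×411×0.5/410 = −0.002, so no value exists.

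**n as family size.** With n = 1.5, N = 412 and ρ = 0.5: sqrt(1 − 2×0.5×0.5/410) = 0.9994, and 0.35 stays 0.350.

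**Simulation.** There were 4,000 runs with 137 families per arm (68 with one parent, 69 with two), ICC 0.5 and a true effect of 0.35. The mean estimate was 0.353 with n = 1.5 and 0.250 with n = 206.

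**The 2-point statement.** The implied SD is 2/0.35 = 5.71. For comparison, an even spread over the integers 0 to 20 has SD 6.06, and the largest possible SD on that range is 10. The SDs below are assumptions, since the documents give none:

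| assumed SD | 0.35 SD in points | 2 points as d |
|---|---|---|
| 3.5 | 1.2 | 0.57 |
| 4 | 1.4 | 0.50 |
| 4.5 | 1.6 | 0.44 |
| 5 | 1.75 | 0.40 |
| 6 | 2.1 | 0.33 |

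**The case against.** The best defence is that the slip can be caught from the text itself. Inside S_T, n_i already counts parents within family i, N is a separate total, and the SAP cites Hedges (2007) with a promise to handle families of different sizes. A careful programmer might put in 1.5. This stands as mitigation. It does not remove the fault, because the only definition in words is the wrong one, and the printed factor has a single n and not the unequal-size form.

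It is also true that the standardised effect is not the primary test. That test is the treatment coefficient in the mixed model, and the SAP promises model estimates with 95% confidence intervals. This limits the consequence to the reported effect size and its interval.

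A reader might infer more from these passages than they support:
- *S_T is a within-family SD, which would inflate the effect size.* The subscript taken alone says so. But the SAP calls S_T a pooled SD within the trial groups, and N−2 is the divisor for two arm means, not for about 275 family means. A subscript slip is the likelier explanation.
- *0.35 SD cannot be 2 points on a 0-20 score.* An SD of 5.7 is large but possible. Because the plan says approximately, any SD above about 4.3 (1.5/0.35) gives a value that rounds to 2.
- *The SD must be narrow because families were selected for behaviour problems.* Eligibility rests on edge-of-care status and age 11-15, with no behaviour threshold.
- *The sample size is wrong.* It reproduces and does not involve points.
- *Significance could be reached below 2 points.* That is true of any trial with 90% power, where the smallest significant estimate is about 1.96/3.24 = 0.60 of the target. It is not a defect of this plan.

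**Conclusion.** The definition of n is wrong as written and should be corrected before the analysis is programmed. With equal arms, n counted per arm and ρ = 0.5, the standardised effect is understated by 29%, and 0.35 becomes 0.25. The size of the error depends on the ICC actually estimated, not on recruitment or dropout. It reaches the primary outcome, all continuous secondary outcomes and the 12-month report. The unstandardised difference, its p-value and N = 412 stand.

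The S_T subscript and the numerator label are clarifications to make at the same time.

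The 2-point equivalence is unsupported but not shown to be false, because it rests on an SD near 5.7 that the documents do not give. The protocol's section on analysis of primary and secondary outcomes names the SDQ total problems score for the primary comparison. The documents do not say whether the 2 points came from that score.

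**What to change.** In the SAP's effect-size text:
- Define n as the average number of parents per family, or print the unequal-cluster-size version that the text promises.
- Write S_T as deviations from each arm's overall mean.
- Label the numerator as the treatment coefficient (γ₂₀ in the primary model).

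In the sample size sections of both documents, state the SD of the externalising score and its source, and restate the point value to match.

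The cost is a wording amendment. Sample size, data collection and the primary test do not change. The 2-point figure may move in either direction once the SD is stated.

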A final Statistical Analysis Plan will be produced prior to any analysis being undertaken and will provide detail of handling missing data. We will explore the impact of missing data on trial outcomes by investigating likely missing data mechanisms and re-fitting the primary outcome within a multiple imputation framework (including exploring MAR and MNAR mechanisms via delta-based controlled multiple imputation).

Procedures for reporting deviation(s) from the original SAP

Any deviations from the original SAP will be submitted as substantial amendments where applicable and recorded in subsequent versions of the protocol and SAP.

Termination of the trial

Beyond the internal pilot, there will be no formal 'stopping rules' or 'discontinuation criteria' for individual participants, parts of trial and entire trial. Any concerns with participant well-being will cross reference this section with those for the TSC as this group is likely to be involved with this decision-making process.

Continuation of the trial from internal pilot to main trial will be decided by the Trial Steering Committee and funder at month 12 (see Internal Pilot Section).

Inclusion in analysis

All randomised participants' data will be included in analysis, if consent has been obtained to use their data and have not withdrawn from the trial, and they have not withdrawn consent to use their data.

Internal Pilot analysis

Statistical analysis for internal pilot feasibility outcomes will be primarily descriptive. Feasibility outcomes will be estimated as frequencies and percentages, means and standard deviations, or medians and interquartile ranges as appropriate. Feasibility outcomes will be assessed against the pre-specified progression criteria. Percentage of missing data will also be reported descriptively.

Analysis of primary and secondary outcomes

Our primary analysis will include all randomised participants who provide outcome data (i.e., a modified intention to treat analysis set) and compare mean scores between arms on the parental SDQ total problems score at 6-months post-randomisation (including both parents' ratings where available) using multilevel models to account for clustering (parents in families), and adjusting for baseline SDQ score, adolescent factors (age, sex, parents in household), and local authority.

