All outcomes will be analysed following the last 6 month follow up post-randomisation (primary end point) and again for the 12 month follow up post-randomisation (addendum report end point) after the database is locked following the last follow up post randomisation. One month after completion of baseline data collection and data cleaning, the database will be locked to new recruitment and only entry of followup data will be permitted.

Timing of outcome assessment

Outcomes	Data collection timepoints			
	Baseline	Treatment Phase	6 month follow-up	12 month follow-up
Adolescent wellbeing self-report: self-report version of the Strengths and Difficulties Questionnaire	X		X	X
Adolescent wellbeing parent/guardian-report: parent-report version of the Strengths and Difficulties Questionnaire	X		X	X

Parenting Scale Adolescent version (PSA, parent completed)	X		X	X
Dyadic Adjustment Scale (DAS-7)	X		X	X
Kessler 6	X		X	X
Warwick-Edinburgh Mental Well-being Scale (SWEMWBS)	X		X	X
Conflict Behavior Questionnaire (CBQ-20)	X		X	X
Closeness subscale of the Child-Parent Relationship Scale (CPRS, short form)	X		X	X
Family APGAR scale	X		X	X
Parenting Self-Regulation Scale	X		X	X
Out of home placement	X		X	X
Self Report Delinquency Measure	X			X

Statistical Principles

Levels of confidence and p-values

All confidence intervals presented will be 95% and two-sided. In addition, applicable statistical tests for the primary analysis will be 2-sided and will be performed using a 5% significance level.

Adjustment of multiplicity

The overall type I error rate for testing support as usual (SAU) plus Standard Teen Triple P (TEEN TRIPLE P) trial arm over the control arm SAU only for the primary endpoint will be controlled at the 2-sided 0.05 significance level (i.e. no correction required as we have a single primary outcome). Secondary analyses will control the family-wise error rate using the Holm method. Secondary outcomes will be analysed and corrected in the following order:

- (1) Parent reported - Adolescent behavioural and emotional problems
- (2) Parenting practices
- (3) Parent and Adolescent reported prosocial behaviours
- (4) Adolescent reported peer relationships
- (5) Interparental outcome
- (6) Parent mental health
- (7) Parent Wellbeing
- (8) Conflict Behavior
- (9) Child-parent relationship
- (10) Family functioning
- (11) Parent self-regulation – the Parenting Self-Regulation
- (12) Delinquency

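### The SAP leaves the primary model's covariates open to observed imbalance; fixing them in advance would use the data better and remove a post-randomisation choice, though the 5% level is not shown to be broken

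*SAP*

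**What the plan says.** The SAP section Primary analysis (6 month) gives the model explicitly: arm, baseline SDQ, local authority and a random intercept for family. Two sections later, Covariate adjustment adds: "We will assess any imbalance of baseline covariates for possible inclusion in the model where large imbalances are noted". The next sentence says that, given the sample size, substantial problems are not expected. Under Descriptive statistics, the SAP rules out significance tests of baseline balance and relies on the clinical importance of any imbalance, so the trigger is a judgement.

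Under Adjustment of multiplicity, the SAP says that type I error for the primary endpoint "will be controlled at the 2-sided 0.05 significance level".

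The Protocol (Analysis of primary and secondary outcomes) specifies a longer fixed list for the primary model: "adjusting for baseline SDQ score, adolescent factors (age, sex, parents in household), and local authority". Age, sex and parents in household are absent from the SAP's model. As the SAP stands, they could enter only through the imbalance paragraph.

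**The concern.** The covariates in the headline analysis should be fixed before anyone sees how the arms compare. The SAP paragraph instead makes them depend on an observed difference between arms, through two undefined terms (possible inclusion, large imbalance). It refers to the model without saying which one, and it is not listed under Sensitivity analyses, so the primary model is not excluded.

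Two things are at stake. First, the primary estimate, interval and p-value could come from a model chosen after by-arm baseline tables were available, which invites challenge even if the choice was innocent. Second, a covariate is worth adjusting for because it predicts the outcome, and that does not depend on whether it happens to differ between arms. A rule triggered by imbalance leaves out prognostic information in every trial where the trigger does not fire.

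**Working it through.** **Inputs from the documents.** The SAP's Sample size section gives "an effect size to be detected of 0.35 with 90% power and a two-sided alpha of 0.05", "an average cluster size within families of up to a maximum of 1.5 parents" and "so also allow for an ICC=0.5", a baseline to follow-up correlation of 0.5, and 20% of families lost. It states 412 parents, 206 per arm. Levels of confidence and p-values adds that "applicable statistical tests for the primary analysis will be 2-sided and will be performed using a 5% significance level".

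**The plan's own figure.**
- Per arm for d = 0.35, 90% power, two-sided 5%: 172.
- Design effect: 1 + (1.5 − 1) × 0.5 = 1.25.
- Baseline adjustment: 1 − 0.5² = 0.75.
- 172 × 1.25 × 0.75 / 0.8 = 201.6 per arm, or 404 in total; 404 to 408 depending on z or t and on rounding. The stated 412 is reproduced to within 3%.
- Effective number per arm at 412: 206 × 0.8 / 1.25 = 131.8. Effect on the baseline-adjusted scale: 0.35 / √0.75 = 0.404. Standard error: √(2/131.8) = 0.123. Ratio 3.281, so power = Φ(3.281 − 1.960) = 90.7%.

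**How often the rule could fire.** With 137 families per arm, the standard error of a standardised baseline difference is √(2/137) = 0.121. One covariate then exceeds 0.2 SD by chance about 10% of the time (0.2/0.121 = 1.66). For three independent covariates, at least one does so with probability 1 − 0.902³ = 27%; for six, 1 − 0.902⁶ = 46%. The result depends heavily on what counts as large. At 132 per arm, the chance is 12% (three covariates) or 23% (six) at 0.25 SD, and 4% or 9% at 0.3 SD.

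**Type I error under no treatment effect.** This was simulated with 20,000 runs per setting (Monte Carlo SE about 0.15 points), 220 analysed families (80% of 275), one or two parents each and ICC 0.5. The documents do not give the following, so they are assumptions: one or six extra covariates, jointly explaining 5%, 15% or 30% of residual variance, and triggers of 0.10, 0.20 or 0.25 SD.

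| Approach | Rejection rate at nominal 5% |
|---|---|
| Covariates fixed in advance, short or long list | 4.8% to 5.2% |
| Every covariate over the trigger is added | 3.1% to 5.0% |
| Smallest p picked after seeing results, one covariate | 5.0% to 6.3% |
| Same, six covariates, trigger 0.20 or 0.25 | 5.6% to 6.8% |
| Same, six covariates, trigger 0.10 | 7.3% to 11.0% |

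The 11.0% needs six covariates explaining 30% of residual variance, a trigger that few would call large, and a search over every subset. In a separate run at 0.3 SD with correlation 0.2 (8,000 runs, Monte Carlo SE about 0.24 points), the rates were 4.4% to 4.7% when the rule was applied mechanically and 4.9% to 5.0% with analyst choice.

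**Power.** Assume three independent covariates, each correlated r with the outcome left after baseline SDQ. Fixed adjustment multiplies residual variance by 1 − 3r².
- r = 0.2: 1 − 0.12 = 0.88. Ratio 3.281/√0.88 = 3.498; power = Φ(1.538) = 93.8%.
- r = 0.1: 1 − 0.03 = 0.97. Ratio 3.281/√0.97 = 3.332; power = Φ(1.372) = 91.5%.

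For r = 0.2, simulated power under the imbalance rule was 91% to 93%, between the short-list 90.7% and the fixed-list value of about 94%. The gap is roughly 1 to 3 points. For r = 0.1, it cannot exceed about 91.5 − 90.7 = 0.8 points.

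**The case against.** A reader might infer that the stated 5% error rate is false. The documents do not support that. The trigger in the SAP is baseline imbalance, not the result, and selection on imbalance alone gave rates at or below 5%. A slightly conservative test still meets a promise to control error at 0.05. Rates above 5% require someone to compare results and choose, and the SAP describes no such step.

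Other points also have force. The SAP expects the clause to matter little, and if large means 0.3 SD or more it would seldom fire. The analysing statistician is stated to be blind. Much of the lost precision comes from the SAP dropping the Protocol's three covariates, which is a separate discrepancy; the rule itself does no worse on power than the SAP's short list.

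These points limit the size of the problem, but the clause is still a selection rule for which a better alternative exists. Nothing requires the covariate choice to come before the outcomes are seen. Baseline tables are to be produced for the as-analysed set too, and that set is known only once 6-month data exist. Blinding would restrain choice by direction of effect, but not by p-value. It is also stated inconsistently: the SAP's Roles and responsibilities table gives the trial statistician's role as Research Fellow/Trial Manager, and the Protocol's Blinding section says the Trial Manager is not blind. Finally, reconciling the two covariate lists would leave the imbalance clause in place.

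**Conclusion.** The point holds as one of pre-specification and efficiency. The SAP allows the primary covariate set to be settled after randomisation by an undefined judgement, while its own model and the Protocol both present the set as fixed. It does not show an inflated error rate. An excess over 5% is possible only with results-informed choice: up to 6.8% at triggers of 0.20 to 0.25 SD, higher only in the extreme setting above, and essentially nil at 0.3 SD.

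The cost in power, against always adjusting for the Protocol's three covariates, is roughly 1 to 3 points if each correlates about 0.2 with outcome and under 1 point at 0.1. Those correlations, the independence of the covariates and the triggers are assumptions; the documents give none of them. This is a free improvement, not a threat to the trial's validity.

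**What to change.** Delete the imbalance sentence as a rule for the primary model. Before unblinding, state that the primary model adjusts for arm, baseline SDQ externalising score, local authority, and the adolescent's age, sex and parents in household, with the family random intercept, whatever balance is observed. This also brings the SAP's covariates into line with the Protocol's. If a covariate outside the list looks imbalanced, a fit that adds it may be reported, but only as a labelled sensitivity analysis.

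The cost is SAP wording. The planned baseline data already cover date of birth, sex and living arrangements, and the sample size does not change. In the simulations, a fixed list held the 5% level within Monte Carlo error.
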